4.2 Withdrawal from study

Patients may be discontinued from the study at any time, at the discretion of the investigator.

Patients are free to discontinue their participation in the study at any time for any reason.

Patients who discontinue from the study should always be asked about the reason(s) for the discontinuation (and informed about their right not to disclose their reason for doing so) and the presence of any adverse events (AEs). If possible, they should always be seen and assessed by an investigator and asked to perform completion outcome measures, including CT, US and QoL questionnaires. A pre-operative CT may be used for follow up should indication to operate the aorta arise. Adverse events should be followed up.

Study treatment should be stopped in the following cases: development of diabetes, persistent renal failure with GFR<45ml/min, severely deteriorating health, aortic surgery or onset of exclusion criteria.

If the study medication is stopped, patients will be asked to remain in the study and follow the other procedures according to the protocol. All randomised patients remain in the group they were originally allocated to for the purpose of intention-to-treat (ITT) analyses.

Patients who discontinue the study will not be replaced.

Sponsor has to be informed if a patient is withdrawn by any reason before study end. The "End of study" form must be filled out by the investigator and the reason should be stated.

The study number will not be reused if a patient is withdrawn.

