5.1.2 Imaging

At baseline, 24 months and completion, the aorta will be examined by non-contrast enhanced CT with 1 mm slices or thinner from the jugulum to the groins.

At enrolment, 24 months and completion the abdominal aorta will be examined by US. The assessment of abdominal aortic diameter with US will be done by the local US technician, using the standardized technique measuring the largest anterior-posterior diameter from leading edge to leading edge perpendicular to the blood flow in the aneurysm. Inclusion criteria will be based on US determined diameter.

If a subject withdraws from the study due to operative need of the aorta, the preoperative CT will be used for analysis in the study. The assessment of aortic diameter on CT will be done using outer edge to outer edge perpendicular to blood flow. Volumetric AAA analysis of CT images will be performed using manual drawing of the vessel wall contours in axial slices of the entire abdominal aortic as well as semiautomatic measures in 3mensio, Pie Medical, Maastricht. Analysis will start at the slice just below the most distal renal artery excluding accessory renal arteries and end at the slice just above the aortic bifurcation. Measures of perivascular adipose tissue will be made adjacent to the aorta.

All CT assessment (diameter and volume) will be done at a core lab at the Department of Radiology, Uppsala university hospital, Uppsala. The CT identification is the four digits enrolment code. The reviewer will be blinded regarding treatment allocation.

CT images will also be reviewed by local radiologists according to GCP at respective hospital. Accidental findings of unrelated pathology on the CT scan will be dealt with as appropriate by investigator at respective site.

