8.2.2 Secondary variables

Secondary efficacy variables are; 1) difference in log-transformed AAA-volume determined by CT at 24 and 60 months vs at baseline (Log-transformation is undertaken because AAA volumes appear to follow a right-skewed distribution based on in house data), 2) difference in AAA-diameter determined by US at 24 and 60 months vs at baseline, 3) difference in circulating inflammation and matrix remodelling biomarkers assessed by established assays, 4) difference in quality of life score at 24 and 60 months vs at baseline, 5) difference in need for AAA surgery and aneurysm rupture at 24 and 60 months and 6) cost effectiveness of metformin treatment 2 g daily to reduce need for prophylactic surgery of AAA.

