8.3 Statistical analysis

The primary efficacy end-point is the between groups difference in mean annual AAA growth over 60 months. AAA growth will be analysed using an analysis of covariance (ANCOVA) model where AAA growth at 60 months is the dependent variable and treatment group and baseline AAA is included as independent variables. The results will be presented as the estimated group difference with 95 % confidence intervals at 60 months.

Similar methods will be used to assess growth as log transformed CT-volume and ultrasound diameter. Analysis of other outcomes: 1) Laboratory data and perivascular adipose tissue are exploratory endpoints and will be reported with descriptive statistics and evaluated with appropriate inferential statistics, 2) Patient reported outcome (QoL questionnaires) will be analysed using non-parametric test (Wilcoxson rank-sum test), 3) Pre-defined clinical events,

such as AAA-repair, rupture and death, are expected to be few, and the presentations will use descriptive statistics, 4) Economic analysis: Will be performed adopting a health system perspective. The cost-effectiveness analysis will produce an incremental cost effectiveness ratio as an estimated cost per surgical procedure avoided.

Handling of missing values: The primary analyses will be performed among patients with a measured value at the specific time point. However, as the number of missing values might be substantial several sensitivity analyses of the primary analysis will be performed:

- Multiple imputation (with different assumptions)
 - Assume that drop-outs respond according to randomized group
 - Assume that drop-outs respond according to control group
- Fixed imputation depending on reason for drop-out
 - For clinical events, such as AAA-repair, rupture and death, impute worst possible value
 - For other events impute using a maximum likelihood function

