10. INTERIM ANALYSIS

When all patients have completed the 24-month follow up (including imaging), an interim analysis will be performed where the primary endpoint, as well as log transformed CT-volume and ultrasound diameter will be analysed using ANCOVA. If there is no trend towards a protective effect (all three p-values for treatment effect >0.2), or a significant harmful effect on AAA growth or AAA related events, the study will be terminated and all on-going metformin treatment stopped.

The decision how to proceed with the study following the interim analysis will be at the discretion of the sponsor.

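### After AAA repair the plan does not settle whether the patient stays in the study or which ultrasound counts, so the ultrasound comparison can use a post-repair reading or lose the patient

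*Combined protocol and SAP*

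**What the plan says.** Four parts of the plan meet on this point.

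- **Does the patient stay?** Section 2.1 defines end of study to include early discontinuation and gives AAA repair as an example. Section 4.2 lists the reasons to stop study treatment: "development of diabetes, persistent renal failure with GFR<45ml/min, severely deteriorating health, aortic surgery or onset of exclusion criteria". It continues: "If the study medication is stopped, patients will be asked to remain in the study and follow the other procedures according to the protocol".
- **Which scans follow?** Section 5.1.2 has: "At enrolment, 24 months and completion the abdominal aorta will be examined by US". CT follows the same later time points. Table 1, footnote 7, places the final ultrasound within a week of the CT.
- **Which scan counts after repair?** Section 5.1.2 says that for a subject who withdraws because the aorta needs an operation, "the preoperative CT will be used for analysis in the study". Section 4.2 says only that a pre-operative CT may be used. Neither names an ultrasound.
- **Who is analysed?** Section 8.3 says "The primary analyses will be performed among patients with a measured value at the specific time point", and adds: "Similar methods will be used to assess growth as log transformed CT-volume and ultrasound diameter". Worst-value imputation for repair appears only among the sensitivity analyses of the primary analysis, for missing values.

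Ultrasound diameter is a secondary variable (8.2.2: "difference in AAA-diameter determined by US at 24 and 60 months vs at baseline"). It also supplies one of the three p-values in the section 10 futility rule, which requires "all three p-values for treatment effect >0.2".

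**The concern.** Repair is triggered by diameter (55 mm for men and 50 mm for women, section 1.1), so repaired patients are disproportionately the fast growers. After repair an ultrasound measures a residual sac or a graft. If such a reading counts as a measured value, a fast grower can enter the analysis as stable or shrinking. If the patient instead leaves without a 24- or 60-month ultrasound, 8.3 omits that patient from the main ultrasound analysis, and the fast growers are lost, more of them from the arm that grows faster. The CT endpoints have partial protection from the pre-operative rule, but it is conditional on withdrawal in 5.1.2 and optional in 4.2. Ultrasound has none.

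At stake are the ultrasound secondary endpoint, one input to the interim decision, and CT diameter and volume for any repaired patient who stays and has a later CT.

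**Working it through.** **Inputs from the plan.** Control growth 3 mm/year, SD 2.17, 30% reduction, 250 per arm, 30% dropout (8.4). Entry diameter 30-49 mm for men (3.1). Repair threshold 55 mm for men (1.1).

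**Plan's own figure.** The target difference is 0.30 x 3 = 0.9 mm/year. Per arm, n = 2 x (1.960 + 0.842)² x (2.17/0.9)² = 2 x 7.849 x 5.813 = 91.3, so 92 per arm and 184 in total, as 8.4 states. The inputs are therefore understood correctly.

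**One patient.** A man enters at 45 mm and grows 3 mm/year. He reaches 55 mm after (55 - 45)/3 = 3.3 years. His pre-repair scan gives (55 - 45)/3.33 = 3.0 mm/year. A 45 mm sac at month 60 gives (45 - 45)/5 = 0.

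**Whole comparison.** Baseline diameter B and annual growth G are simulated, with G ~ N(3, 2.17) for control and N(2.1, 2.17) for metformin. A patient counts as repaired by time T if B + T x G ≥ 55. The analysis is ANCOVA of annual growth on arm and B. For a repaired patient with post-repair reading v, scored growth is (v - B)/T.

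Assumptions not in the documents: B uniform on 30-49 mm, or skewed towards small with mean 36 mm; the values of v; every repaired patient rescanned; the men's threshold for all.

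The share reaching 55 mm by month 60 is about 48% of controls and 34% of metformin patients (uniform), or about 36% and 23% (skewed).

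| Handling of repaired patients, 60 months | Uniform | Skewed |
|---|---|---|
| Pre-repair growth, both arms | -0.90 | -0.90 |
| 55 mm sac, both arms | -0.53 | -0.63 |
| 45 mm sac, both arms | -0.24 | -0.37 |
| No change from baseline, both arms | -0.10 | -0.15 |
| 20 mm graft, both arms | +0.47 | +0.30 |
| Repaired patients dropped, both arms | -0.42 | -0.47 |
| 45 mm sac in metformin arm; controls keep pre-repair growth | -2.1 | -1.7 |
| No change in metformin arm; controls keep pre-repair growth | -2.3 | -2.0 |

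With 250 x 0.70 = 175 per arm, power is about 97% in the first row, 92-94% with a 55 mm sac, 46% or 72% with a 45 mm sac, and 11-17% with no change.

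**If repairs are few.** With 3%, 5% or 10% of controls repaired and all repaired patients scored zero, the difference is -0.76, -0.70 or -0.56. If only metformin patients are scored zero and controls keep pre-repair growth, it is -0.99, -1.05 or -1.20. With no true effect, that last handling produces a false benefit of about -0.23, -0.35 or -0.64.

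**If growth is slower.** With an assumed 1.5 mm/year and SD 1.5 (uniform baseline), about 20% and 14% reach 55 mm, and -0.45 becomes about -0.23 when all are scored zero.

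**Metformin readings scored as no change, repaired controls dropped** (uniform, plan's growth). The result is -0.64 with the plan's effect and -0.51 with no effect. The exaggeration beyond -0.90 thus depends on controls keeping their pre-repair growth.

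**At 24 months.** About 9% of controls (uniform) or 3% (skewed) have reached 55 mm, against 5% or 1% on metformin. Both-arm scoring with a 45 mm sac or no change gives about -0.64 to -0.85.

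**The case against.** The strongest reply is that the plan mostly treats repair as leaving the study. Section 2.1 says so, 5.1.2 speaks of a subject who withdraws for surgery, and 8.3 lists repair among reasons for drop-out. On that reading no post-repair scan exists. Section 4.2 also asks discontinuing patients for completion measures including ultrasound, and footnote 7 would bring a pre-operative ultrasound with the pre-operative CT. This has weight, but it does not close the gap. Section 4.2 still asks patients who stop medication to stay. Nothing says the pre-operative CT is the final CT, or that the completion ultrasound precedes repair. A patient who leaves without an ultrasound is dropped, which the table shows is also biased.

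A reader might infer that the plan scores the fastest growers as stable or shrinking, so that a real effect must shrink or reverse. The documents do not support that:

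- The text permits a post-repair reading but does not direct its use. The measured-value sentence is about missing data, refers to the primary analyses, and reaches ultrasound only through the similar-methods sentence.
- The direction is not fixed. The stay-in sentence is triggered by stopping study medication, which only the metformin arm takes. Read literally, it could keep post-repair readings in that arm alone.
- The wrong sign needs a graft diameter to be entered. Sections 5.1.2 and 8.2.2 describe the diameter of the aneurysm, which a graft hardly fits.

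A reader might also infer that ultrasound could stop the trial at the interim. It cannot do so alone, since futility needs all three p-values above 0.2. With 225 per arm assumed and both arms mis-scored (45 mm sac or no change), the ultrasound p-value exceeds 0.2 in about 2-3% of trials (uniform) or 0.2% (skewed). Only the graft case with uniform baselines is severe.

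Finally, 8.3 expects few repairs, and the 175 per arm already allows for dropout that may include repair, so the larger figures are upper illustrations. The growth inputs are also MRI figures, not ultrasound.

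**Conclusion.** The point holds as a gap with a real but uncertain effect. Sections 2.1 and 4.2 conflict on whether a repaired patient stays, and no rule says which ultrasound counts. On either reading the ultrasound growth comparison can be biased, because repair selects fast growers.

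At 60 months, under the plan's growth figures and the assumed baselines, -0.90 mm/year becomes about -0.10 to -0.63 with both-arm scoring (no change, or a 45-55 mm sac), and about -0.42 to -0.47 if repaired patients are dropped. Keeping such readings in the metformin arm alone, against controls with pre-repair growth, exaggerates the benefit. The distortion is less if repairs are as few as 8.3 expects, though 3 mm/year sits uneasily with that expectation. At 24 months it is small to moderate unless a graft is measured. No single figure should be quoted, since repair rates and post-repair diameters are assumptions. This is a cheap improvement to the plan.

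**What to change.** - Reconcile 2.1 and 4.2 on whether a patient with AAA repair remains in the study, in wording that applies to both arms.
- State in 8.3 and section 10, for both arms, that no CT or ultrasound taken after AAA repair is used as a growth measurement. CT diameter and volume come from the pre-operative CT. Ultrasound diameter comes from the last ultrasound before repair, routine surveillance included. Each change is divided by the actual interval from the baseline scan. Any post-repair scans are descriptive only.
- Make 4.2 and 5.1.2 agree with this, and record the last pre-repair ultrasound and its date in the eCRF.
- Extend the repair sensitivity analysis in 8.3 to ultrasound diameter and CT volume.

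The cost is protocol wording and one eCRF entry. The downside is small: the pre-repair ultrasound falls on a clinically chosen date, so intervals vary and some are short, which makes those annualised rates noisier.

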8.4 Sample size estimation

Based on in house data and original data from an Australian study of the relationship between metformin and AAA growth (Golledge 2017) it is conservatively estimated that metformin treatment will lead to a 30% reduction in annual AAA growth. This is regarded as a meaningful change which is likely to translate to an important reduction in requirement for AAA repair. MRI data from the Uppsala group show a mean growth rate of 3mm/year, SD 2.17. Thus needing 184 patients for 80% power at a 30% reduced growth rate. CT data will likely show 10-15% larger SD, adding a 30% dropout rate over five years we approximate a need to recruit 500 patients, 250 in each arm, for 80% power at 2-tailed α 0.05.

9. CRITERIA FOR TERMINATION OF THE STUDY

The Sponsor reserves the right to discontinue the study prior to inclusion of the intended number of subjects but intends to exercise this right only for valid scientific or administrative reasons. After such a decision, all delivered unused investigational products and other study related materials must be collected without delay and all eCRFs must be completed as far as possible.

The study could be prematurely discontinued in the following cases (examples):

- Unexpectedly high proportion of drug related AEs.
- New findings about the investigational product(s) that changes the benefit/risk ratio.
- Study protocol is difficult to cope with.
- Recruitment of eligible subjects is far too low.
- Unacceptable low investigator or subject compliance.
- Critical change in personnel, administrative or scientific standards at the at the study centre.

10. INTERIM ANALYSIS

When all patients have completed the 24-month follow up (including imaging), an interim analysis will be performed where the primary endpoint, as well as log transformed CT-volume and ultrasound diameter will be analysed using ANCOVA. If there is no trend towards a protective effect (all three p-values for treatment effect >0.2), or a significant harmful effect on AAA growth or AAA related events, the study will be terminated and all on-going metformin treatment stopped.

The decision how to proceed with the study following the interim analysis will be at the discretion of the sponsor.

